Step 2. We surveyed the country with guidance from Ministry of Health publications and consultations, and excluded districts that have or recently had an active maternal health or newborn health intervention, as this would dilute the effect of our intervention or result in high levels of quality of birth care at baseline, with little room for improvement.

Step 3 We combined Western and Southwest Regions into one group and Eastern and East Central Region into a second group in order to consolidate as Western had only 4 possible districts and East Central had only 3.

Step 4. We examined the a) number of facilities by type in each district and b) caseload of births in one year (July 2012- June 2013) in each district, and calculated the average number of births per facility per day. We then selected all districts within the two groups that had an average of > or = to one birth per facility per day. This resulted in 6 districts in the Eastern group and 6 in the Western group.

All public Level II, III, and IV facilities offering birthing services within a district will be included (range of 7-17 per district for a total of 133 facilities). In districts where there is no public hospital, we will include any Private Not for Profit hospital providing birthing services in that district where they exist. In all of these facilities, as mentioned in Section 3c, an estimated 1,300 providers will be included in the study.

District assignment to intervention arm:

In each region we will divide the six districts into two groups of three. Within the groups of three we will randomly choose a district name from a hat. For the district pulled we will draw a number card with a “1”, “2”, or “3” from a hat. Those numbers will correspond with the study arms outlined in Table 1 (page 2).

- Describe the study participants and the population from which they will be/were drawn. If you plan to include children, specify their ages and gender.

Study participants include any providers at selected facilities who provide birthing services to women and all women admitted to the labor ward for labor. (Table 2 presents the maximum number of study contacts per participant.

Table 2. By research objective, Participants (Sample and Population), Data Source, and Number of Contacts

Obj.	Study Participants (Sample & Population)	Data Source	Number of Study Contacts

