- (a) The number of **378 births** is recommended for each time point in the full package group only. N=378 is based on calculations for midline and at endline is based on a (within-group) non-inferiority calculation in the intervention group. We set the number of health facilities at 54 (9 facilities on average per district * 3 districts * each of 2 regions). This sample size will achieve 80% power to detect a non-inferiority margin difference between the group proportions of providing oxytocin of -0.1000. As shown in the previous table, the percent of deliveries with oxytocin provision at midline (post-intervention) is hypothesized to be 70% in Full group. We assume intra-class correlation (ICC) of 0.005 and significance level of the test is 0.0250.
- (b) The number of **189 births** in each group at endline (only) is based on the following assumptions: This is a two-sample comparison of proportions. We aim to detect a 15% point difference at endline between an intervention group and the training-only group. Training-only group value set at 50%, as this is most conservative. Intervention group value set at 65%. Power is set at 80%. ICC is set at 0.01.
- (c) To avoid oversampling, and to compensate for different caseloads at different facilities, the study team will be given a target number of births to observe and they will stop when they reach this target. There will be no overlap in the number of women observed, because different women will be observed at different time points.

Service Statistic Data Abstraction

There is no sample size calculation for analysis of service delivery statistics because baseline data from the study health facilities are not available.

Qualitative Data: Focus Group Discussions and In-depth Interviews

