2. Provider competencies and performance will not decline (i.e. will be non-inferior) between midline and endline in the *partial* package group.
3. At endline, the provider competency level and the performance level of the *partial* package group will be significantly higher than those of the training-only group.
4. At endline, the provider competency level and the performance level of the *full* package group will be significantly higher than those of the training-only group.

Hypotheses 1 and 2:

This is a non-inferiority analysis. Two-sided 90% confidence intervals (CI) for the difference in average knowledge and competence scores between midline and endline will be constructed, separately for full and partial package groups. Non-inferiority will be determined comparing the upper bound of the 90%CI for the difference between the 2 time points to the pre-specified non-inferiority margin of 0.06 (22). If the CI's upper bound is less than the predefined margin, then we are able to claim non-inferiority of the endline knowledge scores to the midline knowledge at a 0.05 level of significance.

We will first examine the differences in sample means of knowledge scores between midline and endline not adjusted for any potential confounding variables. The confidence intervals for the knowledge scores will be calculated using generalized linear models with knowledge and competencies as the dependent variables and time variable (endline vs. midline) as the primary independent variables. To account for repeated observations within providers at midline vs. endline, we will use robust Huber/White estimate of variance implemented in STATA through 'vce' (cluster) option. In addition, adjusted 90% CI for the difference in means will be constructed by adding provider- and facility-level factors in the model.

Hypotheses 3 and 4:

We will examine differences in competencies and performance at endline between the 3 study groups using generalized linear models. The dependent variables in these models will be:

- 1) knowledge and competency scores,
- 2) proportion of women who received **oxytocin** (at correct dosage) within one minute of a vaginal birth,
- 3) proportion of women whose placenta was inspected within 16 minutes, and
- 4) proportion of newborn checked for breathing within 1 minute.

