The primary independent variable will be the study group represented as 2 indicator variables for full and partial training package with training-only as the reference group. For these hypotheses, we will only use endline data. Additional variables, related to provider- and facility characteristics predictive of these outcomes, such as cadre, number of years of provider's experience, and number of prior births attended in last 90 days, will be also included in the model. Analysis of residuals will inform whether the assumptions of the generalized linear model, such as normality and homoscedasticity of residuals as well as linear fit, are satisfied.

Additional analyses will include:

1. At baseline, midline and endline we will collect data from **all study facilities** consisting of service delivery statistics, and facility inventory. These data will be analyzed using population-average marginal generalized linear models estimated using generalized estimating equations (GEE) with exchangeable working correlation structure to account for repeated observations within facilities. The dependent variable will be service delivery statistics. The independent variables will include time (represented as 2 indicator variables for midline and endline with baseline as the reference group), study group (represented as 2 indicator variables for full and partial training groups with training-only as the reference group), and interaction terms (study group by time). The interaction terms will be examined to assess whether there are differences between study groups that change significantly over time.
2. Providers who are trained will keep **logs of their practice sessions**. This is process evaluation data. These data (for example on number of times a scenario is practiced) will be compared across the three study groups using generalized linear models with Poisson or Negative Binomial distribution for the outcome.
3. **Routinely collected data from health facility registers** (recorded daily but aggregated monthly) on services provided to clients and health outcomes (discharge, or deaths and stillbirths) will be analyzed using longitudinal data analysis to account for repeated observations at each facility. This will be for population-averaged marginal generalized linear models using generalized estimating equations (GEE) and exchangeable working correlation structure.

Qualitative Analysis

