We will conduct a doer/non-doer analysis that will contrast providers and managers at facilities that adhere to low-dose/high-frequency practice recommendations with providers at facilities with few or no reported practice sessions. We will also analyze interviews with key stakeholders to identify their recommendations regarding program sustainability. Audio-recordings of focus group discussion and interviews will be transcribed and entered into Atlas.ti software. Data from close-ended questions will be entered into Microsoft Excel or Stata. Pre-determined and emergent codes will be developed, and content analysis will be conducted.

- 6) If human biospecimens (blood, urine, saliva, etc.) will be collected . N/A
- 7) Describe how **subjects** will be **screened for eligibility and assigned to** study/intervention and comparison/control groups.

All providers who attend births at the facilities will be invited to participate. All women who are in labor at the facility on the days of observation will be invited to participate (delivery and newborn care will be observed).

Criteria for being a PPC include: being an experienced skilled birth attendant and likely to remain at the facility during the study period (i.e. no imminent transfers).

- 8) Explain and justify whether there will be **blinding**.

Randomization or blinding of individual subjects is not feasible in this study because of the district-randomized design.

- 9) Explain and justify whether participants **will not receive routine care** or will have current therapy stopped.

Women in labor and delivery (participants) and their newborns will receive routine care as per Ugandan guidelines.

- 10) Explain and justify the use of a placebo or **non-treatment group**.

All study groups will receive the training on Bleeding after Birth and Helping Babies Breathe, and simulators (anatomic models) will be left behind at all facilities. The training-only (comparison) group will be encouraged to practice regularly but will receive no peer support intervention or SMS messages.

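### Arms are assigned to only four districts each, but the endline between-arm models for Hypotheses 3 and 4 make no provision for district clustering

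*Combined protocol and SAP*

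**What the plan says.** Section 3, under district assignment, describes the allocation: "In each region we will divide the six districts into two groups of three". It continues: "Within the groups of three we will randomly choose a district name from a hat", and a numbered card then fixes the arm. With six districts in each of two regions there are four draw sets. If cards are drawn without replacement, each arm receives one district per set, so four in all. Section 4b8 explains the lack of individual randomization and blinding as being "because of the district-randomized design".

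Section 4b5, on Hypotheses 3 and 4, states: "We will examine differences in competencies and performance at endline between the 3 study groups using generalized linear models". The predictors are two arm indicators, with training-only as reference, plus provider and facility characteristics such as cadre, experience and recent births attended. It adds: "For these hypotheses, we will only use endline data".

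The same section does specify correlation handling for other analyses. Repeated provider scores under Hypotheses 1 and 2 get a cluster-robust variance. The service statistics get GEE with an "exchangeable working correlation structure to account for repeated observations within facilities".

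On sample size, Table 5 note (b) in section 3c says: "We aim to detect a 15% point difference at endline between an intervention group and the training-only group". It uses 50% versus 65%, 80% power and 189 births per group. It also says "ICC is set at 0.01", without naming the cluster or its size.

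**The concern.** The treatment varies only between districts, so the information about an arm effect is limited by the number of districts, which is four per arm. A generalized linear model with ordinary standard errors counts each birth or provider as an independent observation. If districts in the same draw set differ for reasons unrelated to the arm, such as staffing, supplies or supervision, that variation passes into the arm contrast but not into its standard error.

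These models carry the claims that the partial and full packages outperform training-only, including on the oxytocin primary outcome. Section 4b10 says the results will inform recommendations to government on scale-up. The consequences would be too many false positive claims, and a stated power that does not belong to a test respecting the assignment. Using endline data only also means that baseline differences between districts are not adjusted for.

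**Working it through.** **Inputs.** Districts: 12 in four sets of three, so four per arm (section 3). Endline births: 189 in the partial and training-only arms and 378 in the full arm (Table 5). Rates: 65% versus 50% (note b); 70% versus 50% for full versus training-only (Table 4). ICC: 0.005 (note a) and 0.01 (note b). Assumed: two-sided 5% level, which note (b) does not state, and the plan's ICCs applied at district level, since the documents give no district ICC.

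**1. The plan's figure of 189.** The two-proportion formula for 50% versus 65% with 80% power gives 170 per group, or 183 with continuity correction. Inflating 183 for ICC 0.01 with *k* clusters per arm uses N = n(1 − ICC)/(1 − n·ICC/k):

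| Clusters per arm | N per arm |
|---|---|
| 54 facilities | 187.5 |
| 133/3 ≈ 44 facilities | 189.0 |
| 36 facilities | 190.9 |
| 4 districts | 334 (293 from n = 170) |

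So 189 is reproduced with facility-sized clusters and not with the district as cluster. At 189 per arm, power falls to 80% at a design effect of 1.116 (pooled variance) or 1.135 (unpooled). At ICC 0.01 that is about 13 to 14 births per cluster. A district contributes 189/4 = 47.25 births, with design effect 1 + 46.25 × 0.01 = 1.4625.

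**2. Size of the unclustered test.** Let *s* be the share of district variance lying within draw sets. The ratio of true to assumed variance is

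R = [(1 − ICC)(1/n₁ + 1/n₂) + 2·s·ICC/4] / (1/n₁ + 1/n₂), and size = 2[1 − Φ(1.96/√R)].

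Example, 189 versus 189, ICC 0.01, s = 1: (0.99 × 0.010582 + 0.005)/0.010582 = 1.463. Then 1.96/√1.463 = 1.62, and the size is 0.105.

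| Comparison | s | Size at ICC 0.005 | Size at ICC 0.01 |
|---|---|---|---|
| 189 v 189 | 1 | 7.7% | 10.5% |
| 189 v 189 | 0.5 | 6.3% | 7.7% |
| 189 v 189 | 0 | 4.9% | 4.9% |
| 378 v 189 | 1 | 8.7% | 12.4% |
| 378 v 189 | 0.5 | 6.8% | 8.6% |
| 378 v 189 | 0 | 4.9% | 4.9% |

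Simulation with four draw sets agreed within one percentage point. In the same runs a district-summary t test stratified by draw set (6 df) had size 4.1% to 5.2%. In a separate simulation, facility-level robust variance alone left the size at about 11% at district ICC 0.01.

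**3. Power with district as the cluster.** At 65% versus 50%, 189 per arm, ICC 0.01: variance = (0.2275 + 0.25)(0.99/189 + 0.01/4) = 0.003695, SE = 0.0608, and 0.15/0.0608 = 2.47. Degrees of freedom are 12 − 3 = 9 unstratified, 8 with region and 6 with draw set.

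| Scenario | Normal | 9 df | 6 df |
|---|---|---|---|
| H3, 65 v 50, ICC 0 | 84.7% | 75.7% | 70.2% |
| H3, 65 v 50, ICC 0.005 | 76.7% | 66.9% | 61.4% |
| H3, 65 v 50, ICC 0.01 | 69.4% | 59.5% | 54.3% |
| H4, 70 v 50, 378 v 189, ICC 0.01 | 95.4% | 89.9% | 85.7% |
| H4, 70 v 50, 189 v 189, ICC 0.01 | 91.8% | 84.6% | 79.7% |

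With half the district variance between draw sets, Hypothesis 3 on 6 df at ICC 0.01 has 62% power.

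**4. Side check on note (a).** Its 54 facilities come from 9 × 3 × 2, which implies six districts per arm; four districts give 9 × 4 = 36. Non-inferiority power moves only from 84.0% to 83.4%, so the mismatch is one of consistency.

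**The case against.** The section is headed as a brief plan, its covariate list is open-ended, and it never says observations are independent. On that reading the cluster handling is merely unstated. This has limited force: the same section spells out correlation handling for other analyses, and note (b) uses an ICC for this very comparison, so the gap falls on the one test that needs it most.

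The magnitude is the stronger ground. Since 189 is reproduced with facility-sized clusters, 0.01 is probably a facility ICC, and placing all of it at district level is then a ceiling under the plan's assumptions. If half of it lies between districts (about 44 facilities per arm, no gain from draw sets), size is 7.9% for 189 versus 189 and 9.0% for 378 versus 189. If a quarter does, it is 6.6% and 7.2%. This stands as a caution on the figures, but nothing in the documents stops the true ICC from exceeding 0.01; at an assumed district ICC of 0.02 the size is about 16% for 189 versus 189.

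Omitting the draw-set term does not itself inflate the error. With variance between sets only, the unclustered test rejected 4.6% of the time. That term serves precision and fidelity to the assignment.

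Two points on power also stand. Table 5 lists 189 for the full arm's endline-only comparison. An endline model would naturally use all 378 births, but if only 189 enter, Hypothesis 4 falls just below 80% on 6 df. And Table 4 expects 60%, not 65%, in the partial arm at endline; at 60% versus 50%, Hypothesis 3 has only about 50% power with no clustering at all.

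**Conclusion.** The concern holds and must be fixed before the endline analysis. That the models omit the unit of assignment is clear from the text. The size of the effect is conditional: for district ICCs of 0.005 to 0.01, true size runs from about 5% (all district variance between draw sets) to 10.5% for partial versus training-only and 12.4% for full versus training-only. Planned covariates may lower these, but they do not correct the standard error for assignment by district.

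For Hypothesis 3 at note (b)'s rates and ICC 0.01, power is about 69% by normal approximation and 54% to 60% on 6 to 9 df. Part of that drop comes from the small-sample test itself, since power is already 70% to 76% at ICC 0. Hypothesis 4 stays at 86% to 95% if all 378 full-arm births are used.

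**What to change.** - In section 4b5, specify that Hypotheses 3 and 4 are analysed with district as the cluster and draw set (or region) as the stratum, by a small-sample method suited to binary outcomes. Options are district-level summaries with a t test (6 df by draw set, 8 df by region), or GEE or a mixed model with a small-sample correction. Facility clustering alone, or uncorrected robust errors on 12 districts, would not be enough.
- In Table 5 note (b), state which cluster the ICC refers to and the test level. Restate power as a range over assumed district ICCs, and show Table 4's 60% for the partial arm beside the 65%. State whether 189 or 378 full-arm births enter the between-arm model.
- As a minor correction, bring note (a)'s facility count into line with four districts per arm: 36 at nine each, or about 44 from 133/3.

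The cost is plan wording, wider intervals and a less favourable stated power for Hypothesis 3. No added enrolment is asked for, and the change does not bring Hypothesis 3 back to 80%.

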16	Semi-structured interview guide: Health care providers	Health care providers will be asked about their experiences with the program and their ideas for how to improve care for postpartum hemorrhage and neonatal asphyxia.
17	Semi-structured interview guide: Stakeholders	Stakeholder will be asked about their opinions about how to strengthen and sustain this program and other efforts to improve care for postpartum hemorrhage and neonatal asphyxia in Uganda.

3) *Number of study contacts* or visits required of participants.

Please see table 2 on page 5 for details. Briefly, women in labor, key stakeholders and facility in-charges will each have a maximum of only one study contact. Providers could have up to 12 study contacts, if they were selected for all types of data collection, but this will be rare. Similarly, peer practice coordinators could have up to 12 study contacts plus regular telephone contact with a member of the research team.

4) **Expected duration of the study.**

After JHSPH IRB and Ugandan IRB are obtained, the study will take 18 months.

5) A brief **data analysis plan** and description of the **nature of the variables** to be derived.

Primary Outcome:

- For the postpartum hemorrhage component, the primary outcome will be the proportion of women who received **oxytocin** (at correct dosage) within one minute of a vaginal birth, before delivery of the placenta. Data for this outcome will be obtained from the direct clinical observations.
- For the neonatal asphyxia component, the primary outcome will be the proportion of babies not breathing at birth who are breathing or being ventilated by one minute.

Secondary Outcomes:

- Change in providers' knowledge and competence related to postpartum hemorrhage and neonatal resuscitation, as assessed by knowledge tests and observed performance with a simulator.
- Trends in PPH and neonatal asphyxia/mortality rates, by abstracting *aggregated* monthly service statistics from each facility.
- Identification of structural, environmental and behavior factors that are associated with routine, frequent practice with the simulator.

Data will be entered using [name]/Foxpro/SPSS/CsPro and analyzed using Stata 12.

Quantitative data analysis

Specific Hypotheses:

In BAB and in HBB related to the primary outcomes (see Section 4b5):

1. Provider competencies and performance will not decline (i.e. will be non-inferior) between midline and endline in the *full* package group.

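### Hypotheses 3 and 4 each list at least four endline outcomes without saying which decides, and the list omits the declared asphyxia primary

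*Combined protocol and SAP*

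**What the plan says.** Section 4b5 names one primary outcome per component. For postpartum hemorrhage (BAB) it is oxytocin at the correct dose within one minute of vaginal birth. For asphyxia (HBB) it is the proportion of babies not breathing at birth who are breathing or being ventilated by one minute. Knowledge and simulator competence are listed as secondary: "Change in providers' knowledge and competence related to postpartum hemorrhage and neonatal resuscitation, as assessed by knowledge tests and observed performance with a simulator".

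The specific hypotheses (Section 1, repeated in 4b5) are headed "In BAB and in HBB related to the primary outcomes (see Section 4b5". Hypothesis 3 reads "the provider competency level and the performance level of the *partial* package group will be significantly higher than those of the training-only group"; Hypothesis 4 says the same of the full package.

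The analysis paragraph for both hypotheses begins "We will examine differences in competencies and performance at endline between the 3 study groups using generalized linear models" and numbers the dependent variables (DVs):

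1. "knowledge and competency scores"
2. oxytocin within one minute
3. placenta inspection
4. "proportion of newborn checked for breathing within 1 minute"

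Each package arm is compared with training-only through an indicator variable. No alpha, sidedness, testing order, adjustment or combining rule is given for these tests.

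**The concern.** Three of the four listed items are not declared primaries, and one of the two declared primaries is not listed. A reader cannot tell from the plan what result would confirm or refute Hypothesis 3 or 4. If any listed outcome may count, a significant placenta-inspection or knowledge result could be reported as support while oxytocin shows no difference. If all must be significant, the 80% power stated for oxytocin does not describe the power of the hypothesis. For HBB, no listed performance outcome is the declared primary. This matters because Section 4b10 says the results will inform recommendations to government on scale-up.

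**Working it through.** **Step 1: does the text already name a decider?** The heading ties the hypotheses to the primary outcomes, but other parts of the plan prevent it from working as a rule.
- The heading covers BAB and HBB, yet the HBB primary is absent from the list.
- Hypotheses 1 and 2 carry the same heading, yet their confidence intervals and margin are described only for knowledge and competence scores, which are secondary.
- Objective 3 in Section 1 defines provider performance by three measures (uterotonic, placenta inspection, breathing check). These are close counterparts of DVs 2–4, so the word performance in the hypotheses does not single out oxytocin.
- The hypotheses name competency alongside performance.

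**Step 2: which alpha?** None is stated, so I tested what reproduces the plan's 189 births per group. Inputs from Section 3c, Table 5 note (b): 50% vs 65%, 80% power, ICC 0.01. Note (a) gives 54 facilities, so 189/54 = 3.5 births per facility.
- Two-sided 0.05, mean proportion 0.575: n = [1.96·√(2·0.575·0.425) + 0.8416·√(0.5·0.5 + 0.65·0.35)]² / 0.15² = 169.3.
- With continuity correction: (169.3/4)·[1 + √(1 + 4/(169.3·0.15))]² = 182.4, rounded up to 183.
- Design effect 1 + (3.5 − 1)·0.01 = 1.025, and 183·1.025 = 187.6, so 188 against the stated 189.
- With the same design effect, one-sided 0.05 gives 138 (151 with correction) and two-sided 0.025 gives 212 (225).

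Two-sided 0.05 is therefore consistent with the sizing, but it is an inference.

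**Step 3: error for one arm contrast under each reading.** The documents give no correlations between test statistics, so 0, 0.5 and 0.8 are assumed. With independence, P(at least one of k) = 1 − (1 − α)^k. The other values come from 1,000,000 draws of equicorrelated normal statistics. Favourable means in favour of the package arm, with a nominal rate of 0.025.

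| Reading | Nominal | Corr. 0 | 0.5 | 0.8 |
|---|---|---|---|---|
| Declared primary of one component decides (two-sided) | 0.05 | 0.05 | 0.05 | 0.05 |
| Any of four (two-sided) | 0.05 | 0.186 | 0.156 | 0.114 |
| Any of four (favourable) | 0.025 | 0.096 | 0.078 | 0.057 |
| Score and any of DVs 2–4, nothing works (favourable) | 0.025 | 0.002 | 0.010 | 0.017 |
| Same, DV 1 split into four scores (favourable) | 0.025 | 0.007 | 0.026 | 0.032 |
| Any of DVs 2–4, competency truly improves (favourable) | 0.025 | 0.073 | 0.062 | about 0.05 |
| All four required, nothing works (favourable) | 0.025 | <0.001 | 0.001 | 0.005 |

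The competency-improves row treats the score test as certain to be significant, so only the performance tests can err: 1 − 0.975³ = 0.073 under independence. If DV 1 is four scores (knowledge and OSCE, for BAB and HBB), there are seven tests. Any one counting then gives 0.301, 0.230 and 0.148 (two-sided).

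**Step 4: power if all four are required.** If each outcome had 80% power, joint power would be 0.8⁴ = 41% under independence, 56% at correlation 0.5 and 66% at 0.8. This is illustrative only, because the plan states power for oxytocin alone.

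**The case against.** The strongest reply is that the plan already signals the answer. It declares one primary per component, heads the hypotheses with a reference to them, classes competence as secondary, and sizes the birth observations on oxytocin alone. If oxytocin decides the BAB part, that part has no inflation. This is good evidence of intent, but the four points in Step 1 keep it from being a decision rule, above all for HBB.

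A second reply is that the hypotheses join competency and performance, so a false claim needs a result in each domain. That stands when nothing works: the error is then 0.002 to 0.032 against 0.025. It does not protect the performance claim when simulator skills improve and care at birth does not, which is a plausible outcome for this programme.

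A third reply is that placenta inspection and the breathing check are not stray measures, since Objective 3 prespecifies them. That is correct. It explains why they are listed, but it does not say what weight they carry.

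A reader might infer that each hypothesis will be called supported about three times too often. The documents do not support that. It requires the reading in which any one outcome suffices, which no passage states and which fits the joint wording least, together with an alpha that is inferred and correlations that are assumed.

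**Conclusion.** The gap is real. Hypotheses 3 and 4 have no stated deciding outcome, and the list that serves them leaves out one of the two declared primaries. What follows is an undefined error rate, not a demonstrated inflation. For one arm contrast it runs from no inflation (a component's primary decides, or all outcomes are required) to about 11–19% if any of four counts. Under the joint wording it is near or below nominal when nothing works, and about 5–7% against 2.5% for a false favourable performance claim when only competency improves. These figures assume two-sided 0.05 per test and correlations of 0 to 0.8. They cover multiplicity across outcomes only, not clustering or the use of two arm contrasts. The change is worth making before the endline analysis.

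**What to change.** In the Hypotheses 3 and 4 paragraph of Section 4b5, and in the matching hypothesis text in Sections 1 and 4b5:

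- State that the performance part is decided, separately for each component, by that component's declared primary at a stated two-sided 0.05. For BAB this is oxytocin within one minute. For HBB it is non-breathing newborns breathing or ventilated by one minute, which must be added to the list.
- Word the claims by component. If either primary could carry a whole hypothesis, the error would be 1 − 0.95² = 9.75% under independence.
- Report placenta inspection, the breathing check and the knowledge and competency scores as secondary, with estimates and 95% confidence intervals.
- If a confirmatory competency claim is wanted, name one score per component and test it only after that component's primary is significant.

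The BAB comparison keeps its oxytocin-based sizing. The alternative of splitting alpha over four outcomes (0.0125 each) would cut power for oxytocin at 189 births to about 62% with continuity correction (66% without), and would need about 261–264 births per group to restore 80%.

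The cost is wording, with no new data. A significant secondary result alone can no longer carry Hypothesis 3 or 4. The HBB primary uses only newborns not breathing at birth, a subset of the observed births whose size the plan does not give, so its estimate is likely to be imprecise and the plan should say so.
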